5.1.2 Trial site personnel assigned trial-related duties

The principal investigator may define appropriately qualified personnel at a trial site to perform significant trial-related procedures and/or to make trial-related decisions under his/her supervision. In this case, the principal investigator must maintain a signed list of the persons to whom they delegate significant trial-related duties/responsibilities; the delegated trial-related duties/responsibilities must be specified in the list.

When personnel or responsibility changes are made, the principal investigator must ensure that the relevant documentation is updated before any trial-related activities are performed.

Documentation of all involved trial site personnel performing significant trial-related procedures and/or making trial-related decisions must be maintained according to GCP and applicable regulatory requirements.

5.2 Contract research organizations

Contract research organizations (CRO; commercial, academic or other, e.g., local laboratory facilities, trial supply management provider, electronic CRF provider) may be contracted by the sponsor to perform trial-related duties and functions. The extent of the delegation must be documented. All involved CROs will be required to have implemented quality control and quality assurance processes, and to support the sponsor's quality control and quality assurance measures.

Documentation of all involved CROs must be maintained according to GCP and applicable regulatory requirements. Documentation of any delegation of responsibilities to CROs must be maintained in the trial master file.

5.3 The sponsor and sponsor's personnel

The trial sponsor listed on the title page accepts the responsibilities of the sponsor according to GCP and applicable regulatory requirements.

The sponsor must designate appropriately qualified personnel to advise on trial-related topics. The trial site will be provided with contact details for these personnel before any trial-related procedure is performed.

A list of key sponsor personnel involved in the preparation of this protocol and the conduct of the trial, including their full names, titles, roles, and responsibilities, must be maintained.

If non-sponsor monitors are involved in the monitoring of this trial, a list of all non-sponsor monitors including their full names, addresses, and responsibilities, must be maintained.

6 INTRODUCTION AND TRIAL BACKGROUND

6.1 Introduction

The American Society of Anesthesiologists Task Force on Acute Pain Management (2004) states in its update report of the practice guidelines for acute pain management in the perioperative setting that literature supports the administration of 2 analgesics that act by different mechanisms via a single route to provide superior analgesic efficacy with equivalent or reduced adverse effects. The Task Force believes that NSAID, selective cyclooxygenase-2 inhibitor (COXIB), or acetaminophen administration has a dose-sparing effect for systemically administered opioids. Whenever possible, doctors should use the strategy of multimodal or balanced analgesia aiming to individualize therapy of acute pain. This consensus group has suggested that the development of new drug combinations or routes of administration are opportunities to improve pain management meeting the individual needs of every patient.

6.3 Trial rationale

The combination of analgesics is a common therapeutic practice (e.g., in ZALDIAR which combines tramadol HCl and acetaminophen/paracetamol). Combining tramadol with diclofenac is expected to provide the beneficial analgesic effects of the 2 products. The components are anticipated to be complementary. Pre-clinical studies and clinical trials in inflammatory pain models showed that the combination of tramadol and diclofenac has a synergistic and additive effect that allows its administration at tramadol HCl 25 mg and diclofenac sodium 25 mg doses, with analgesic efficacy and safety in inflammatory pain conditions (Rodríguez-Silverio et al. 2011, Auad Saab et al. 2009, Auad et al. 2009).

This trial is conducted in order to complete the dossier on the tramadol HCl/diclofenac sodium FDC to obtain the registration in the Latin American countries. It is expected to demonstrate the safety and efficacy of the FDC product in comparison to the respective monotherapies.

7 TRIAL OBJECTIVES AND ENDPOINTS

The overall objective of the trial is to evaluate the analgesic efficacy and safety of the tramadol HCl/diclofenac sodium FDC at 2 dose levels (50 mg/50 mg, 25 mg/25 mg) in comparison to the monotherapy of diclofenac sodium 50 mg and tramadol HCl 50 mg.

The specific primary and secondary trial objectives as well as primary and secondary endpoints are listed in Section 1.2.

The primary endpoint is defined in detail in Section 7.1.

7.1 Definition of primary endpoint

Pain relief will be assessed at 15, 30, 45, 60, and 90 minutes, and at 2, 3, 4, 5, 6, 7, 8, and 16 hours after first dose using a 5-point verbal rating scale (VRS) with categories 0 (none), 1 (a little), 2 (some), 3 (a lot), or 4 (complete) (see Section 12.2.1.2).

The primary endpoint of the trial will be 4-hour Total Pain Relief (TOTPAR4). TOTPAR4 is a time-weighted measure of AUC up to 4 hours and is a summary measure that integrates serial assessments of a subject's pain over the duration of 4 hours after first dose.

TOTPAR4 scores will be calculated as $\sum PR_{t=4} \times [\text{time (hours) elapsed since previous observation}]$ where $PR_{t=4}$ is the Pain Relief at time point $t = 4$ in comparison to the assessment before administration of IMPs (Max and Laska 1991). For the first pain relief assessment, time (hours) elapsed since previous observation is time since first dose of IMP. Pain relief assessments after start of rescue medication intake (Section 10.5) will be set to missing and will be imputed as described in the statistical section (see Section 14.5.5).

Minimum and maximum potential value for TOTPAR4 are 0 and 16 points, corresponding to a value of 0 (none) or 4 (complete) at all pain relief assessments in the first 4 hours after first dose, respectively.

8 TRIAL DESIGN

This is a prospective, randomized, double-blind, diclofenac- and tramadol-controlled, parallel-group, multi-site, interventional Phase III trial to evaluate the analgesic efficacy and safety of administrations of tramadol HCl/diclofenac sodium FDCs (25 mg/25 mg and 50 mg/50 mg) in subjects with acute moderate to severe pain after third molar extraction.

8.1 Discussion of the trial design

The analgesic control of acute moderate to severe pain after third molar extraction is a well-established model to demonstrate safety and efficacy of analgesic anti-inflammatory drugs (Barden et al. 2004). The randomized design and the use of matching placebos permit a fair and unbiased comparison of the tramadol HCl/diclofenac sodium FDC at 2 levels (25 mg/25 mg and 50 mg/50 mg) with the monotherapies diclofenac sodium 50 mg and tramadol HCl 50 mg.

The TOTPAR was selected as primary variable as it is most sensitive to detect pain differences (Singla et al. 2015). The analysis after 4 hours (TOTPAR4) minimizes the impact an additional intake of rescue medication might have. Furthermore, an analysis after 4 hours allows a comparison of the efficacy of the FDC with the efficacy of the monotherapies (diclofenac or tramadol) before plasma levels drop below published minimum effective concentrations (data on file, Phase I trial for Adorlan).

The tramadol HCl/diclofenac sodium FDC 25 mg/25 mg is currently registered and marketed under the tradename Adorlan Comprimidos® or Adorlan Tabletas® in 7 countries in Latin America for the relief of mild to moderate inflammatory pain: Colombia, Dominican Republic, Ecuador, El Salvador, Guatemala, Honduras, and Panama.

The selection of the endpoints for the trial matches the requirements laid down in the drafted Guidance for Industry on Analgesic Indications: Developing Drug and Biological Products (Feb 2014).

8.1.1 Rationale for the IMPs and the selected doses

The selected treatments and the doses for the FDC of tramadol and diclofenac were chosen based on the experience gathered in previous clinical trials (Auad Saab et al. 2009 and Auad et al. 2009).

Diclofenac sodium 50 mg and tramadol HCl 50 mg were chosen as comparators since the Mexican and Brazilian Legislation on Fixed-dose Combinations recommends comparing the FDC with the individual components of the combination.

Ibuprofen 400 mg was selected as rescue medication because it has shown efficacy in a randomized double-blind trial in the post-surgical model of extracted third molars (Bakshi et al. 1994). Ketorolac tromethamine 30 mg (intramuscularly) was selected as second-line rescue medication for subjects who do not experience sufficient pain relief with ibuprofen.

8.1.2 Rationale for the number and the frequency of visits/assessments

The frequency of the assessments was based on the literature available for previous trials with other kinds of drugs using the dental pain model (third molar extraction).

8.2 Benefit/risk analysis

Subjects participating in this trial will benefit as the medical need of required third molar extraction is covered as well as the proper management of the pain associated with this procedure. The risks are implied in the surgical procedure of dental extraction as pain and bleeding. Adverse events of the drug combination are described in the investigator's brochure. It is expected that their frequencies will be similar to or lower than those with the individual drugs.

The investigators must become familiar with all sections of the investigator's brochure, the ibuprofen product information, and the ketorolac product information prior to initiation of the trial.

9 SUBJECT ENROLLMENT AND TRIAL DISCONTINUATION

9.1 Subject enrollment procedure

Subjects will be screened to identify those who could potentially be enrolled into the trial. Potentially eligible subjects will be asked to enroll into the trial by giving written informed consent.

If required by applicable regulatory requirements, the principal investigator must keep suitable logs of the subject enrollment procedure.

9.1.1 Handling of low enrollment

Trial sites with a low recruitment rate and/or which persistently deviate from the protocol may be required by the sponsor/coordinating investigator/sponsor's authorized delegate to stop further recruitment at once or to cease participation in the trial.

An activated site can be considered to have a low recruitment rate if it has not allocated a subject to treatment within 6 weeks, i.e., less than 6 subjects in 6 weeks, after trial treatment was available at the trial site.

9.2 Inclusion/exclusion criteria

The trial population must comply with the inclusion/exclusion criteria given in Section 1.3.

Subjects will only receive IMP if documentation is available showing that they comply with all of these criteria.

9.3 Subject discontinuation from the trial or IMP

Once a subject enrolls in this trial, whilst protecting subject safety, the trial site should make every effort to retain the subject for the planned duration of the trial.

A subject may withdraw consent at any time.

9.3.1 Subject discontinuation from the trial

If subjects are not eligible to be allocated to the IMPs, they must be classified as enrollment failures and be discontinued from the trial. It is at the discretion of the investigator to discontinue subjects from the trial if they cannot comply with the requirements of the protocol.

A subject must be discontinued from the trial if any of the following criteria are met after enrollment.

- Subject meets exclusion criteria at Visit 2.
- Subject withdraws consent.

9.3.2 Subject discontinuation from the IMPs

The principal investigator may decide to discontinue a subject from the IMPs if she/he considers continued treatment of the subject to pose an undue risk to the subject, e.g., due to particular adverse events. All subjects treated with IMPs must be followed up within the trial until the end of the trial, the subject's death, their withdrawal of consent, or loss to follow-up.

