1.3.2 Exclusion criteria**1.3.2.1 Exclusion criteria at Visit 1**

1. Findings in the medical record, vital signs, and/or physical examination demonstrating abnormal conditions of subject's general state of health preventing his/her participation in the clinical trial according to the investigator's opinion.
2. Subject unable to speak, read, or write in Spanish language.
3. Clinical laboratory parameters exceed the pre-defined alert ranges (i.e., 1 standard deviation above or below the upper/lower limit of the normal ranges).
4. Known hypersensitivity to the IMPs, the anesthetic to be used during surgery, or to the rescue medication (ibuprofen, ketorolac).
5. Known alcohol or drug abuse in the last 6 months or any history of seizures. Alcohol abuse is defined as the consumption of more than 3 ounces (about 90 mL) of liquor or spirits or 18 ounces (about 530 mL) of beer per day, for 5 consecutive days during the 6-month period. Drug abuse is defined as the use of any recreational drug for 5 consecutive days during the 6-month period.
6. Subjects who take analgesic medication for chronic pain, monoamine oxidase inhibitors, tricyclic antidepressants, neuroleptics, or other drugs that reduce the seizure threshold within 4 weeks of enrollment.
7. Pregnant or lactating women.
8. Subjects who received systemic corticosteroids or opioid analgesics less than 2 weeks before surgery.
9. Subjects with molars linked to the mandibular canal.
10. Subjects requiring immediate dental procedures other than third and fourth molars extraction.

1.3.2.2 Exclusion criteria at Visit 2

11. Subject received a long-acting non-steroidal anti-inflammatory drug (NSAID) within 24 hours or 5 times the elimination half-life of that drug prior to surgery, whatever the longer.
12. Subject received any analgesic medication other than short-acting pre-operative or intra-operative anesthetic agents within 24 hours before taking IMPs.
13. Subject received more than 300 mg of lidocaine in total.
14. Subject received any analgesic medication other than the IMPs immediately after the oral surgical procedure was completed.
15. Baseline pain intensity of the subject after oral surgical procedure remains below 5 points on the 11-point numerical rating scale (NRS).

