9.3.3 Procedure for the handling of discontinued subjects

9.3.3.1 Handling of subjects who discontinued from the trial

The principal investigator must document any discontinuation of a subject and inform the sponsor. Where applicable, the relevant IECs must be informed with a detailed written explanation.

The following must be done for **all** discontinued subjects, including those who withdrew informed consent:

- Document the main reason for discontinuation from the trial.
- Ensure that all data collected until the day of discontinuation is transferred to the CRF.
- Ensure that any dispensed pain assessment booklet is returned.
- Ensure that any unused IMPs and rescue medication (including all packaging) is returned.
- If possible, perform all tests as defined for the End-of-treatment Visit (Visit 3).
- Complete any other trial-related formalities, e.g., those related to discharge from the trial site.
- For subjects withdrawing consent, document in the source data the date and time of withdrawal.
- Document in writing, if a subject withdraws consent but agrees to attend the End-of-treatment Visit (Visit 3) and the Final Visit (Visit 4).

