An elective hospital admission, e.g., for pre-planned surgery, will not be considered an SAE if documented at enrollment. Short-lasting (<24 hours) hospital admissions, e.g., for clinical check-ups, not meeting any of the other above mentioned criteria will also not be considered SAEs.

Special procedures for serious adverse events

If SAEs occur that are not tolerable, the investigator will decide for that subject whether to stop the trial and/or treatment of the subject. For further details, see Section 9.3.

Expectedness of adverse events

Expectedness will be assessed by the sponsor.

An unexpected adverse event is one where the nature or intensity is not consistent with the information in the investigator's brochure.

Furthermore, reports that add significant information about the specificity or severity of a known, already documented adverse reaction constitute unexpected adverse events. For example, an adverse event more specific or more severe than expected would be considered "unexpected".

Definition of adverse drug reactions

An adverse drug reaction is any untoward and unintended response to an IMP or a medicinal product related to any dose administered.

A list of adverse drug reactions seen for the IMPs is given in the reference safety information, i.e., in the investigator's brochure.

Documentation of adverse events

The subjects will be questioned about possible adverse events with non-leading questions before administration of the IMP and at regular intervals thereafter as defined in Section 1.8.

All adverse events reported spontaneously by subjects at any time point will also be documented.

All adverse events will be documented in the CRF with the following information where appropriate:

- Description (adverse event reported term)
- Start date/time

- End date/time or continuation.
- Whether adverse event was serious.
- Intensity
- Outcome
- Action taken with IMPs.
- Countermeasures
- Causal relationship to IMPs.

Definition of intensity

The clinical intensity of an adverse event will be classified as:

Mild:	Signs and symptoms that can be easily tolerated. Symptoms can be ignored and disappear when the subject is distracted.
Moderate:	Symptoms cause discomfort but are tolerable; they cannot be ignored and affect concentration.
Severe:	Symptoms which affect usual daily activity.

For adverse events where the intensity changes over time, the maximum intensity observed during the whole duration of the adverse event will be documented.

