
Adverse events occurring in the Enrollment Period but before first administration of an IMP and worsening on or after IMP administration will be documented as new adverse events.

Definition of outcome at the time of last observation

The outcome at the time of last observation will be classified as:

- Recovered/Resolved
- Recovering/Resolving
- Not recovered/Not resolved
- Recovered/Resolved with sequelae.
- Fatal
- Unknown (unknown should only be used, if at the time of the last visit for a subject in a trial, the outcome of the adverse event is unknown to the investigator, e.g., because the subject is lost to follow-up).

In the event of irreversible congenital anomalies, the choice “not resolved” should be used. “Fatal” should only be used when death is possibly related to the adverse event (note: the causal relationship of the IMP to the adverse event is not to be considered for this decision). If there is more than 1 adverse event, only the adverse event leading to death (possibly related) will be attributed with the outcome “fatal”.

Definition of countermeasures

“Countermeasures” will be defined as:

None:	No countermeasure given.
Newly started medication:	A newly started medication or change in dose or route of application of a medication due to the adverse event (to be listed on the prior/concomitant medication page) that is used as a countermeasure.

Trial discontinuation:	It was necessary to discontinue the subject from the trial due to the adverse event.
Other:	All other countermeasures, e.g., physical therapy, surgery.

Except for none, multiple countermeasures for 1 adverse event can be recorded.

Classification of action taken with IMPs when an adverse event occurs:

- Dose reduced.
- Drug interrupted.
- Drug withdrawn.
- Dose not changed.
- Not applicable.
- Unknown.

Classification of causation

The causal relationship of an adverse event to IMPs will be classified using the following terminology. The given criteria for each term are for consideration and are neither exhaustive nor required to be fulfilled in total for the selection of the respective term:

Terms for classification of causation	Criteria for the selection of causality classification terms
Conditional/ Unclassified:	Additional data for a proper assessment are under examination.
Unassessable/ Unclassifiable:	The available data cannot be judged because information is insufficient or contradictory, and cannot be supplemented or verified.

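### Treated subjects can be removed from the trial for reasons Section 9.3.2 does not allow, and those removed have no required Day 14 contact

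*Protocol*

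**What the plan says.** The retention rule is in Protocol Section 9.3.2: "All subjects treated with IMPs must be followed up within the trial until the end of the trial". The only earlier end points it lists are death, consent withdrawal and loss to follow-up. Section 3.2 defines the verb used there as always mandatory.

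Other parts of the protocol provide for treated subjects to leave on further grounds:

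- **Section 9.3.1, discretion.** "It is at the discretion of the investigator to discontinue subjects from the trial if they cannot comply with the requirements of the protocol". Nothing limits this to subjects not yet dosed.
- **Section 9.3.1, obligation.** "A subject must be discontinued from the trial if any of the following criteria are met after enrollment". The two triggers are meeting a Visit 2 exclusion criterion and withdrawing consent.
- **Section 12.3.1, serious adverse events.** For events that are not tolerable, "the investigator will decide for that subject whether to stop the trial and/or treatment of the subject". The reader is then referred to Section 9.3.
- **Section 12.3.1, countermeasures.** One category is trial discontinuation, defined as "It was necessary to discontinue the subject from the trial due to the adverse event".

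Protocol 14.5.5 and SAP 8.3.1 replace pain relief scores that are missing after premature discontinuation from the trial. The replacement value depends on arm and on whether the reason was lack of efficacy, an adverse event, or something unrelated to the drug.

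Follow-up then differs by route. Section 9.3.3.1 (off the trial) asks for data up to the day of discontinuation and for Visit 3 tests where possible. It mentions the Final Visit only for subjects who withdraw consent but agree to attend. Section 9.3.3.2 (off IMP, still in the trial) makes Visit 3 and the Day 14 contact mandatory.

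**The concern.** Two subjects with the same adverse event after the first dose can be handled differently, depending on whether the site records the stop as a stop of IMP or as a removal from the trial. The first must be contacted on Day 14; for the second the protocol prescribes no such contact. Comparing the safety of the combination with that of the monotherapies is a stated objective, so uneven capture of new events matters, particularly if removals differ between arms.

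The same choice affects the primary endpoint. The second dose is not due until 8 hours and subjects stay on site at least that long. The 0–4 hour scores therefore reflect the first dose alone and can normally be obtained whatever is decided about later doses. If the subject is taken off the trial, the remaining scores need not be collected, and a fixed value that depends on arm and recorded reason takes their place.

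**Working it through.** **1. The sections side by side**

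| Ground for leaving the trial after dosing | Allowed by 9.3.2? | Provided for elsewhere? |
|---|---|---|
| Death, consent withdrawal, loss to follow-up | Yes | Consistent |
| Cannot comply (investigator's discretion) | No | 9.3.1 |
| Serious adverse event, or adverse event | No | 12.3.1, in two places; imputation category |
| Lack of efficacy | No | Imputation category only |
| Visit 2 exclusion criterion found after dosing | No | 9.3.1 |

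Section 9.3.3.2 also lists checking the discontinuation criteria among the steps that need not be done once a subject is off IMP. This implies that the criteria are otherwise checked after dosing.

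**2. What is lost from TOTPAR4**

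The inputs are the relief schedule in Protocol 7.1 (0.25, 0.5, 0.75, 1, 1.5, 2, 3 and 4 h), weights equal to the time since the previous score, and δ = 0 or 0.375 from Protocol 14.5.5. The weights are 0.25 × 4 + 0.5 × 2 + 1 × 2 = 4 h, and 4 h × 4 gives the stated maximum of 16.

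The plan's own figure reproduces. Discontinuation at 2 h leaves 2 h of weight unobserved, and 2 × 0.375 = 0.75 = 1.5/2, which is half the margin.

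| Removed just after | Scores lost | Weight lost | Share of 4 h | Credit at δ = 0.375 |
|---|---|---|---|---|
| 1 h | 4 | 3 h | 75% | 1.125 |
| 2 h | 2 | 2 h | 50% | 0.75 |
| 3 h | 1 | 1 h | 25% | 0.375 |
| 4 h or later | 0 | 0 | 0% | 0 |

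**3. Effect on an arm mean**

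The documents give no removal rate. I assume 1–3% of an arm (2–6 of 200), all removed just after the 1 h score, with unobserved relief of 2 for the remaining 3 h.

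- Loss per subject with δ = 0: 2 × 3 = 6 points.
- Loss per subject with δ = 0.375: 6 − 1.125 = 4.875 points.
- Fall in the arm mean with δ = 0: 0.01 × 6 = 0.06 to 0.03 × 6 = 0.18.
- Fall in the arm mean with δ = 0.375: 0.01 × 4.875 = 0.05 to 0.03 × 4.875 = 0.15.

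The larger figure, 0.18, is 12% of the 1.5-point margin (0.18/1.5), and it requires every removal to fall in one arm. If a monotherapy and a combination arm both lost 3% for lack of efficacy or adverse events, the residual difference would be 0.03 × 1.125 = 0.03 points, against the combination. With δ = 0 in both arms it would be zero. Removals for non-compliance would presumably be coded as unrelated to the drug, so δ = 0 in every arm. If they fell only in a monotherapy arm, the shift would favour the combination in the tests that use that arm.

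**The case against.** The strongest reply is that Section 9.3.2 is the specific rule for treated subjects and governs wherever the text is loose. On that view, 9.3.1 opens with subjects not eligible for allocation and is about enrollment failures. The serious adverse event paragraph refers back to Section 9.3, and the countermeasure category merely records what happened and can be used for events before dosing. Section 9.3 also tells sites to try to keep subjects in the trial. The imputation categories could be filled partly by subjects who withdraw consent because of pain or an adverse event.

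Part of this stands. The countermeasure field grants no authority to remove anyone, and no single passage is decisive. But the reference to Section 9.3 leads to 9.3.1 as well as 9.3.2, so it does not settle which applies. The retention effort is worded as a recommendation under the protocol's own definition. No text limits the discretionary rule, the serious adverse event option or the countermeasure to undosed subjects.

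Four stronger readings are tempting, and the documents do not support them.

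- *The protocol obliges investigators to remove treated subjects.* The Visit 2 criteria concern surgery and the period before dosing, for example "Subject received any analgesic medication other than short-acting pre-operative or intra-operative anesthetic agents within 24 hours before taking IMPs", and are checked before allocation. They reach a treated subject only if a violation is found after dosing. The other trigger, consent withdrawal, is already an exception in 9.3.2.
- *Removed subjects have no safety follow-up.* Section 12.3.1 follows any known adverse event to resolution, stability or clinical judgment, without excluding discontinued subjects. What is missing is a required contact that would find new events.
- *About 12 of 13 days go uncovered.* Nothing is scheduled between Visit 3 and Day 14 for anyone. The specific Day 14 shortfall is one contact.
- *A 6-point loss dwarfs the 1.5-point margin.* The first is one subject's score, the second a difference in means.

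**Conclusion.** The inconsistency is real and should be resolved. Section 9.3.2 requires treated subjects to be kept in follow-up with three exceptions; Sections 9.3.1 and 12.3.1 allow further removals; the imputation rules plan for them; and 9.3.3.1 then leaves those subjects without a required Day 14 contact.

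The main consequence is for detection of new adverse events in subjects removed by the investigator. Its size cannot be given, because the documents state no expected number. For TOTPAR4 the effect is probably small, about 0.06–0.18 points on one arm's mean. This rests on the assumed 1–3% removed at 1 hour, relief of 2 thereafter and δ = 0. Only removals before 4 hours count, and balanced removals largely cancel. Rescue use is not a route to removal, since Section 10.5 asks those subjects to complete the procedures. The planned sample size is unaffected.

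**What to change.** 1. Reconcile Protocol 9.3.1, 9.3.2, 9.3.3.1 and the two places in 12.3.1, together with the discontinuation categories in Protocol 14.5.5 and SAP 8.3.1. The text should state whether, and how, removal from the trial applies once a subject has been dosed. Which clinical rule is right is for the sponsor and investigators; this point does not address their decisions on treatment or participation.
2. Amend 9.3.3.1 so that every treated subject who has not withdrawn consent or refused still has the remaining scheduled pain assessments (where feasible), Visit 3 and the Day 14 safety contact.

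The cost is amendment wording and, for a few subjects, some further assessments and a phone call. Subjects with eligibility violations found after dosing would stay in follow-up. The FAS already includes them if they have at least one relief score in the first 4 hours, so the analysis sets do not change.
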